8.0 Drugs and Devices

8.1 * DRUGS AND/OR BIOLOGICS: Are you **STUDYING any drugs and/or biologics that are either approved or unapproved: (REQUIRED)**

Yes No

Note: This question is frequently answered incorrectly. If any drugs or biologics, approved or unapproved, are being administered under this protocol, you should check 'Yes' unless you are absolutely sure that NONE of the drugs are part of the research protocol. Tip: Ask the PI or the sponsor if you are not sure how to answer this question.

8.3 * MEDICAL DEVICES: Are you **STUDYING any medical devices, in vitro diagnostics, or assays that are either approved or unapproved: **(REQUIRED)****

Yes No

8.4 * NSR: Are you requesting a Non-Significant Risk (NSR) determination for an investigational device: **(REQUIRED)** Note: an NSR determination is different from an Investigational Device Exemption (IDE). Check the Help link for more guidance on what types of devices can qualify for an NSR determination.

Yes No

8.5 LIST THE DEVICES: List the medical devices or in vitro diagnostics to be studied or used. In the device details screen you will be asked questions such as:

- Whether the device is FDA approved or investigational
- Medicare device category
- If the device will be provided at no cost
- If an IDE is necessary, the IDE number, and who holds the IDE
- Risk category of the device
- FDA status of the device

Please see the [UCSF IRB website](#) for more details about the use of devices in research, including the [Investigator Checklist for Significant Risk, Non-Significant Risk, and/or IDE Exempt Device Studies](#)

Verification of IDE numbers: If the sponsor's protocol does not list the IDE number, you must submit documentation from the sponsor or FDA identifying the IDE number for this study. Attach this documentation in the Other Study Documents section of the Initial Review Submission Packet.

If you have any correspondence from the FDA or sponsor regarding this device, please attach it to the application.

View Details	Device Name	Is the Device FDA Approved	Is this a new device or a new use of an already approved device	IDE Number
	iHealth Wireless Smart Gluco-Monitoring System	Yes	No	

Manufacturer/Supplier of Device	iHealth Labs
Medicare Category	 A  B
Where will the Devices Be Stored	
Will Devices be supplied at no Cost	Yes
Is this a HUD (HDE)	No
HDE Number	
Is the Device FDA Approved	Yes
Is this a new device or a new use of an already approved device	No
Is an IDE necessary	No
IDE Number	
Who holds the IDE	N/A
IDE details	

In the opinion of the sponsor, select the level of risk associated with this device	No Significant Risk		
 Livongo In Touch Blood Glucose Monitoring System	Yes	No	
Manufacturer/Supplier of Device	Livongo		
Medicare Category	 A  B		
Where will the Devices Be Stored			
Will Devices be supplied at no Cost	Yes		
Is this a HDE (HDE)	No		
HDE Number			
Is the Device FDA Approved	Yes		
Is this a new device or a new use of an already approved device	No		
Is an IDE necessary	No		
IDE Number			
Who holds the IDE	N/A		
IDE details			
In the opinion of the sponsor, select the level of risk associated with this device	No Significant Risk		

8.6 * Is this an expanded access or compassionate use protocol, meaning the primary purpose is to diagnose, monitor or treat a patient's condition, rather than the collection of safety and efficacy data of the experimental agent: (REQUIRED)

Yes No

9.0 Sample Size and Eligibility Criteria

9.1 ENROLLMENT TARGET: How many people will you enroll:

300

If there are multiple participant groups, indicate how many people will be in each group:

Livongo Health system (experimental group) - 150
iHealth glucose meter (control/standard group) - 150

9.3 SAMPLE SIZE JUSTIFICATION: Explain how and why the number of people was chosen. For multi-site studies, this is referring to the number that will be enrolled across all sites:

- Sample size:
 - *Null Hypothesis:* There is no association between use of Livongo and change in A1c.
 - *Alternative Hypothesis:* (two-sided): The use of Livongo is associated with change in A1c.

- Effect size (t-test) = 0.5%
- Evidence:
 - A1c decreased from 7.9% to 7.5% in 3 month study of mobile phone-based data service (Kollman, et al., 2007, J Med Internet Res, 9:e36)
 - A1c decreased from 8.4% to 7.85% (adults) and 8.52 to 8.06% (children) in 6 month study using a multi-access diabetes management service (Lanzola, et al., 2007, J Diabetes Sci Technol, 1:730-7)
 - Difference in change in A1c -0.35 (intervention) vs +0.15 (control) after 12 months of using an automated diabetes management system (wireless glucose transfer) (Toscos, et al., 2012, Diabetes Care, 35:498-502)
- Standard deviation = 1% (based on the above publications)
- Standardized effect size = E/S = 0.5
- Using a two-sided t-test of 0.05 and power of 80%, n=63 participants per group

We anticipate that we will be able to recruit 300 participants (150 in each arm). Using the above parameters, the study would have 80% power to detect a minimum effect size of 0.33% (and 90% power to detect a minimum effect size of 0.38%).

9.4 * PARTICIPANT AGE RANGE: Eligible age ranges: (REQUIRED)

- 0-6 years
- 7-12 years
- 13-17 years
- 18-64 years
- 65+

9.5 * STUDY POPULATIONS: Data will be collected from or about the following types of people (check all that apply): (REQUIRED)

- Inpatients
- Outpatients
- Family members or caregivers
- Providers
- People who have a condition but who are not being seen as patients
- Healthy volunteers
- Students
- Staff of UCSF or affiliated institutions
- None of the above

9.6 * SPECIAL SUBJECT GROUPS: Check the populations that may be enrolled: (REQUIRED)

- Children / Minors
- Subjects unable to consent for themselves
- Subjects unable to consent for themselves (emergency setting)
- Subjects with diminished capacity to consent
- Subjects unable to read, speak or understand English
- Pregnant women
- Fetuses
- Neonates
- Prisoners
- Economically or educationally disadvantaged persons
- None of the above

If not already addressed in the Background and Significance questions in the Research Plan section or elsewhere, explain why it is appropriate to include the types of subjects checked above in this particular study:

There is a chance that a person who is economically or educationally disadvantaged may have the opportunity to join the study as long as they fulfill all of the inclusion criteria and do not meet any of the exclusion criteria. It is important to allow these participants to join the SUGAR Study because this population, much like others who may participate in the study, may also:

1. Utilizes smartphone and mobile phone technology in daily life, and
2. Suffers from diabetes and can benefit from additional diabetes management.

Describe the additional safeguards that have been included in the study to protect the rights and welfare of these subjects and minimize coercion or undue influence:

Here are some examples:

- evaluating capacity to consent for individuals who may be decisionally impaired (specify how)
- calibrating payment amounts to be non-coercive for the financially disadvantaged
- conducting more in-depth evaluations of subjects' understanding of the study and the voluntary nature of participation
- involving advocates in the consent process

More information and other safeguards are described here: **Vulnerable Subject Populations** and **Recruiting Staff and Students**.

As mentioned in this application, all participants will receive equal treatment, resources (depending on their treatment group), and all active and compliant participants will receive equal payment (see Section 13) during their participation. Additionally, all participants are able to read the consent form before joining the study and are always given the option to opt-out of the study after enrolling. During the enrollment and recruitment phase, participants will sign up for the study on their own volition and will not be forced or coerced to participate. All study activities are completely voluntary.

9.7 INCLUSION CRITERIA: Briefly describe the population(s) that will be involved in this study. Include anyone that data will be collected from or about (e.g. patients, healthy controls, caregivers, providers, administrators, students, parents, family members, etc.):

- People with type 2 DM on any type of medication
- Self-reported A1c level $\geq 7\%$
- Adults, age ≥ 18 years
- Not using continuous glucose monitoring or an insulin pump
- iOS Smartphone with access to data and/or Wi-Fi

9.8 EXCLUSION CRITERIA: List any exclusion criteria (e.g. reasons why someone would not be included in the study):

- Using continuous glucose monitoring during the study period
- People with type 1 DM
- Self-reported A1c level $< 7\%$
- Using an insulin pump during the study period
- Unable or unwilling to switch BG meters to the study meter
- Hospitalization for DKA or hypoglycemia in the past 1 month prior to enrollment
- Pregnant patients, or intention to become pregnant during the study period
- Participants who are currently using, or have ever used, the Livongo Health Program

9.9 * RESEARCH CONDUCTED ON PATIENT CARE WARDS: Do any study activities take place on patient care units at UCSF medical facilities: (REQUIRED)

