7.0 Research Plan and Procedures

7.1 This new consolidated section requests information about:

- Hypothesis
- Aims
- Study Design

- **Background and Significance**
- **Preliminary Studies**
- **Procedures**
- **Statistical Methods**
- **References**

Later sections include:

- **Drugs and Devices**
- **Sample Size, Eligibility, and Subjects**
- **Recruitment and Consent**
- **Risks and Benefits**
- **Data and Safety Monitoring Plan**
- **Confidentiality, Privacy and Security**
- **Financial Considerations**
- **Qualifications of Personnel**
- **Other Approval and Registrations**

7.2 HYPOTHESIS: Describe the hypothesis or what the study hopes to prove (Help Text updated 9/13):

We hypothesize that use of the Livongo Health system results in a greater improvement in hemoglobin A1c (A1c) compared to standard blood glucose (BG) monitoring, measured by the iHealth Bluetooth-enabled glucose meter.

7.3 AIMS: List the specific aims:

To determine the effect of use of the Livongo Health system versus standard BG monitoring in adults with type 2 diabetes on glycemic control as measured by A1c. As a secondary outcome, we will determine the effect of use of the Livongo Health system on fasting lipid panels.

7.4 DESIGN: Briefly describe the study design (e.g., observational, interventional, randomized, placebo-controlled, blinded, cross-over, cross-sectional, longitudinal, pharmacokinetic, etc.):

The study is a two-arm randomized controlled trial (RCT). Participants will either be randomized to receive the Livongo Health system or the iHealth glucose meter for measuring their blood glucose.

7.5 BACKGROUND AND SIGNIFICANCE: Briefly provide the background and significance of this study (e.g. why is this study needed) (space limit: one half page):

The goal of Livongo Health (<http://www.livongo.com/>) is to help people with diabetes and other chronic conditions better manage their health by using a combination of patented technology, smart analytics, and a coaching team. For the purposes of this study, Livongo will provide a comprehensive diabetes care solution that involves unlimited test strips, real-time glucose monitoring with real-time feedback and support of coaches. We will compare this comprehensive system with current standard blood glucose (BG) monitoring with the iHealth Bluetooth glucose meter and standard diabetes care.

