- Once the baseline A1c value is obtained, the patient will be randomized (block randomization by diabetes type).

3. Device Usage

- After randomization, participants will receive either the Livongo Health system or the iHealth glucose meter by mail.
 - If a participant is randomized to the iHealth treatment group, participants will download the iHealth iOS application (iHealth Gluco-Smart) and receive an iHealth blood glucose meter in the mail. Participants will link the iHealth application with a mobile version of the Eureka mHealth Research Platform.
 - If a participant is randomized to the Livongo system treatment group, the participant will receive the Livongo blood glucose meter device in the mail, create a Livongo account, and link their Livongo account with the Eureka mHealth Research Platform.
- Livongo- or iHealth-specific instructions will be provided with each meter and a study coordinator will be available to answer study participant questions about using the BG meters. Participants may be referred to Livongo or iHealth customer service for technical support, if needed.
- Participants will not be given specific instructions on how often to check their BG, or how often they should use the Livongo system or iHealth glucose meter as a part of this study. This is done in order to determine the uptake of the intervention and resulting behavior without outside prompting.
- Participants will either use the Livongo system or the iHealth glucose meter for 6 months from the time of enrollment in the study.

4. Messaging/Reminders

- Participants who have been mailed a BG meter but are not using the device after two weeks will be contacted by in-app push notifications, text messages, email or a phone call for device setup and/or assistance.
- Participants will also receive reminders to complete study activities via in-app push notifications, text messages, email or a phone call.
- Two weeks prior to the end of the study period, participants will be contacted by email and/or receive in-app push notifications to remind them to complete their A1c measurement and closeout surveys.

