Note: Participation in this research study will not affect individual participants' standard clinical care for diabetes. Participants will remain under the care of their current health care provider and will be able to continue receiving all usual care from that provider. The health care provider will continue to provide recommendations for the number of times the participant should check their blood glucose. Although the participant will be asked to use a different glucose meter for this study, the number of times they

use it will still be determined by their health care provider. The same information that they received from their existing glucose meter will be available from the study glucose meter. During the study, they will be provided with glucose meter strips at no charge, to ensure that an insufficient number of strips will not interfere with their standard of care.

7.11 INSTRUMENTS: List all questionnaires, surveys, interview, or focus group guides that will be used for this study:

If the instruments are not complete or not available because they will be developed as part of this study, describe the basic content or include an outline and submit the final versions to the IRB with a modification for approval prior to use.

Survey instruments:

- Intake Survey + General Diabetes Status
- Basic Demographics
- Social Demographics
- Internet Use
- Diabetes Distress
- Physical Activity (IPAQ)
- Quality of Life (SF-12)
- Hospital Visit and Health Care Provider
- Diabetes Empowerment

Attach any unpublished instruments in the 'Other Study Documents' section of the Initial Review Submission Packet form after completing the study application. Published instruments should NOT be attached.

7.12 * BIOSPECIMEN COLLECTION: Are you drawing any blood or collecting other biosamples (e.g. tissue, buccal swabs, urine, saliva, hair, etc.): (REQUIRED)

Yes No

* Could this study generate genetic data that may be broadly shared (e.g., submitted to NIH in compliance with **Genomic Data Sharing (GDS)/Genome-Wide Association Studies (GWAS)** requirements): (REQUIRED)

Yes No

Based on current research trends, we strongly recommend including the genomic data sharing language in the consent form to allow future sharing, even if you don't anticipate it now. It's easier than trying to reconsent all the specimen donors!

7.13 * TYPE OF SPECIMENS (check all that apply): (REQUIRED)

- Blood
- Tissue (describe below):
- Existing/archival materials (name source below): --

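### Section 9.3's 0.5% effect is not drawn from evidence on the contrast tested here; name baseline A1c as a covariate in 7.25 and rest 9.3 on its own 0.33%/0.38% detectable effects

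*Combined protocol and SAP*

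**What the plan says.** Section 9.3 (Sample Size Justification) enters "Effect size (t-test) = 0.5" (in A1c percentage points) with SD 1%, two-sided 5% significance and 80% power, and obtains 63 per group. It lists three sources:

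- "A1c decreased from 7.9% to 7.5% in 3 month study of mobile phone-based data service"
- "A1c decreased from 8.4% to 7.85% (adults) and 8.52 to 8.06% (children) in 6 month study"
- "Difference in change in A1c -0.35 (intervention) vs +0.15 (control) after 12 months", which 9.3 describes as wireless glucose transfer

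It attributes the SD to the same publications. It then says that 300 can be recruited, 150 per arm, and adds: "Using the above parameters, the study would have 80% power to detect a minimum effect size of 0.33" percentage points, with 0.38 for 90% power.

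The titles in 7.26 (References) place the first source in type 1 diabetes and the third in children with type 1 diabetes. Sections 9.7 and 9.8 restrict this trial to adults with type 2 diabetes and exclude type 1. Section 7.9 sets 6 months of use.

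The control condition in 7.2 is standard monitoring "measured by the iHealth Bluetooth-enabled glucose meter". In 7.9, "Participants will link the iHealth application with a mobile version of the Eureka mHealth Research Platform", and the closing note says of participants, without limiting it to one arm, that "they will be provided with glucose meter strips at no charge". The experimental arm, in 7.5, adds real-time feedback, a coaching team with educators on call, and unlimited strips.

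Section 7.25 (Statistical Methods) proposes mixed-effects models or generalized estimating equations for change in A1c. It says that confounders may be adjusted for but does not name them. Baseline A1c appears there only as a possible stratifier, split at 7.0%.

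**The concern.** A two-group t-test needs a difference between arms. A before-after fall equals that difference only if the control arm does not change, and 9.3 neither says this nor gives a control-arm change for two of its three sources. The third source does give a between-arm figure, but in a different population, over twice the follow-up, and with 0.15 of its 0.50 coming from a worsening control arm.

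The control arm here also has a connected meter and free strips, so some improvement in it is plausible. In the other direction, 9.3 mentions coaching in none of its sources, and coaching is a core part of the Livongo programme.

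At stake is how a result near zero would be read. Taken at face value, 63 per group against 150 planned suggests more than twice the needed sample. That margin exists only if 0.5% is the right target. The figure that matters is the smallest difference 150 per arm can detect, and 7.25 leaves open the simplest way to reduce it.

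**Working it through.** **Inputs from 9.3:** difference 0.5, SD of change 1.0, two-sided alpha 0.05, 150 per arm. **Assumed, because the documents do not give them:** any control-arm change, any added effect of coaching, the correlation r between baseline and follow-up A1c, and any loss to follow-up.

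**1. The plan's own figures.** n per arm = 2(1.960 + 0.842)² × 1² / 0.5² = 62.8, so 63. The exact t-test gives 64, which is the same for practical purposes. The detectable difference at 150 per arm is (1.960 + 0.842) × 1 × √(2/150) = 0.323 for 80% power, or 0.325 by the t-test. For 90% power the values are 0.374 and 0.376. The stated 0.33 and 0.38 agree after rounding up; power at those values is 81% and 91%.

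**2. What the evidence gives.** The falls in treated groups are:

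- 7.9 − 7.5 = 0.40
- 8.4 − 7.85 = 0.55
- 8.52 − 8.06 = 0.46
- 0.35 in the controlled trial

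The only between-arm figure is 0.35 + 0.15 = 0.50.

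**3. How power depends on the unstated control change** (150 per arm, SD 1%, t-test, no covariate):

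| Assumption | Difference | Power |
|---|---|---|
| Control flat | 0.35 / 0.40 / 0.46 / 0.55 | 86 / 93 / 98 / 99.7% |
| Control falls 0.1 | 0.25 / 0.30 / 0.36 / 0.45 | 58 / 74 / 87 / 97% |
| Control falls 0.2 | 0.15 / 0.20 / 0.26 / 0.35 | 25 / 41 / 61 / 86% |

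In the other direction, an assumed extra 0.1 from coaching with a flat control gives differences of 0.45 to 0.65 and power of 97% or more. The documents favour no row.

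**4. What adjustment for baseline A1c gives.** Let baseline and follow-up have equal variance σ² and correlation r. The variance of change is 2σ²(1 − r). Setting it to 1, as in 9.3, gives σ² = 1 / [2(1 − r)]. The variance left after regression on baseline is σ²(1 − r²) = (1 + r)/2. The detectable effect therefore scales by √[(1 + r)/2]:

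| r (assumed) | Residual SD | 80% detectable, 150 per arm | 80% detectable, 120 per arm (assumed loss) |
|---|---|---|---|
| no covariate | 1.000 | 0.325 | 0.36 |
| 0.3 | 0.806 | 0.262 | 0.293 |
| 0.5 | 0.866 | 0.281 | 0.314 |
| 0.7 | 0.922 | 0.299 | 0.335 |

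For example, at r = 0.5 and 150 per arm: 0.3245 × 0.866 = 0.281. At that r, power for a difference of 0.30 rises from 74% to 85%, and for 0.25 from 58% to 70%.

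**The case against.** The strongest reply is that the trial is not really sized on 0.5%. Section 9.3 enrols 300 because that many can be recruited, and it discloses what 300 can detect. This stands: questioning the source of 0.5% changes no enrolment number.

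A reader might infer that the trial is underpowered, or that enrolment must rise. The documents do not support that. Every fall cited in 9.3, set against a flat control arm, gives at least 86% power at 150 per arm. The low values in the table need a control-arm fall that no section supplies.

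A reader might also see two connected-meter arms with little left between them. Section 7.5 does not support that either. The experimental arm has coaching, educator contact triggered by high and low readings, and immediate feedback. The control link in 7.9 goes to the research platform, and no section says that control readings reach a coach or clinician. The note in 7.9 says the study meter gives participants what their own meter already gave, and presents free strips as protecting usual care. Coaching could make the true difference larger than the cited sources suggest.

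Finally, 7.25 already allows adjustment, and 7.5 calls the study a pilot. Both are true, but an unnamed covariate set is not a pre-specified analysis, and a pilot label does not turn before-after falls into a between-arm estimate.

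**Conclusion.** The point holds as a weakness in justification. As described in 9.3, the evidence for 0.5% is two before-after falls and one 12-month trial in children with type 1 diabetes, so it does not estimate this trial's contrast. The arithmetic is right, and 0.33%/0.38% are valid for 150 analysed per arm at SD 1%. Whether the true difference lies below or above 0.5% cannot be settled from the documents.

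What can be improved without that knowledge is precision. Pre-specified adjustment for baseline A1c lowers the 80% detectable effect from 0.325 to 0.26-0.30 (0.28 at r = 0.5). This rests on SD of change 1%, equal variances at baseline and follow-up, an assumed r of 0.3 to 0.7, and no loss. The gain is measured against an analysis of change without baseline and is smaller when r is higher. Adjustment does not supply the missing evidence for 0.5%; it makes the trial depend less on it.

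**What to change.** **In 7.25**, replace the open reference to confounders with a named term: the primary longitudinal model of change in A1c includes baseline A1c as a continuous covariate. Any other covariates should be listed in advance. Section 7.9 requires the baseline value before randomization, so every randomized participant should have it. If baseline enters as a covariate, it should not also be a row of the outcome.

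**In 9.3**, as an accompanying text change, rest the justification on the 0.33%/0.38% detectable effects at 150 per arm and label them as assuming no loss. Do not lead with 63 per group at 0.5%.

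**Cost:** two text edits. There are no extra patients, visits or measurements, and no increase in enrolment is proposed.
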